	90th	111	112	114	115	117	119	119	73	73	74	75	76	77	78	78	
	95th	115	116	117	119	121	122	123	77	78	79	80	81	81	82	82	
	99th	122	123	125	127	128	130	130	85	86	86	88	88	89	90	90	

Blood Pressure Levels for Boys by Age and Height Percentile (Continued)

Age (Year)	BP Percentile ↓	Systolic BP (mmHg)							Diastolic BP (mmHg)						
		← Percentile of Height →							← Percentile of Height →						
		5th	10th	25th	50th	75th	90th	95th	5th	10th	25th	50th	75th	90th	95th
11	50th	99	100	102	104	105	107	107	59	59	60	61	62	63	63
	90th	113	114	115	117	119	120	121	74	74	75	76	77	78	78
	95th	117	118	119	121	123	124	125	78	78	79	80	81	82	82
	99th	124	125	127	129	130	132	132	86	86	87	88	89	90	90
12	50th	101	102	104	106	108	109	110	59	60	61	62	63	63	64
	90th	115	116	118	120	121	123	123	74	75	75	76	77	78	79
	95th	119	120	122	123	125	127	127	78	79	80	81	82	82	83
	99th	126	127	129	131	133	134	135	86	87	88	89	90	90	91
13	50th	104	105	106	108	110	111	112	60	60	61	62	63	64	64
	90th	117	118	120	122	124	125	126	75	75	76	77	78	79	79
	95th	121	122	124	126	128	129	130	79	79	80	81	82	83	83
	99th	128	130	131	133	135	136	137	87	87	88	89	90	91	91
14	50th	106	107	109	111	113	114	115	60	61	62	63	64	65	65
	90th	120	121	123	125	126	128	128	75	76	77	78	79	79	80
	95th	124	125	127	128	130	132	132	80	80	81	82	83	84	84
	99th	131	132	134	136	138	139	140	87	88	89	90	91	92	92
15	50th	109	110	112	113	115	117	117	61	62	63	64	65	66	66
	90th	122	124	125	127	129	130	131	76	77	78	79	80	80	81
	95th	126	127	129	131	133	134	135	81	81	82	83	84	85	85
	99th	134	135	136	138	140	142	142	88	89	90	91	92	93	93
16	50th	111	112	114	116	118	119	120	63	63	64	65	66	67	67
	90th	125	126	128	130	131	133	134	78	78	79	80	81	82	82
	95th	129	130	132	134	135	137	137	82	83	83	84	85	86	87
	99th	136	137	139	141	143	144	145	90	90	91	92	93	94	94
17	50th	114	115	116	118	120	121	122	65	66	66	67	68	69	70
	90th	127	128	130	132	134	135	136	80	80	81	82	83	84	84
	95th	131	132	134	136	138	139	140	84	85	86	87	87	88	89
	99th	139	140	141	143	145	146	147	92	93	93	94	95	96	97

BP, blood pressure

\* The 90th percentile is 1.28 SD, 95th percentile is 1.645 SD, and the 99th percentile is 2.326 SD over the mean.

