2. STUDY DESIGN

2.1 General Study Design

Study SHP465-308 is a Phase 3, open-label, multicenter, 12-month safety and tolerability study of SHP465 in children (aged 4-12 years, inclusive, at the time of consent was obtained in the antecedent study [SHP465-112 or SHP465-309] or at the time of consent into this study if directly enrolled) with ADHD.

Approximately 80 subjects will be enrolled into this study. Subjects enrolled in this study will be divided into 2 groups based on participation in antecedent studies as follows:

- Subjects in Group A are those who have been rolled over from antecedent studies (SHP465-112 or SHP465-309). These subjects do not need additional screening and washout procedures.
- Subjects in Group B will be directly enrolled subjects who will be required to undergo full screening and washout procedures before first dose.

Antecedent study SHP465-112 is a Phase 1 study in subjects aged 4-5 years who were administered 6.25 mg SHP465. Antecedent study SHP465-309 is a Phase 3 study in subjects aged 6-12 years who were randomized to either 6.25 mg SHP465 or placebo.

For subjects in Group A, the baseline defined in the antecedent study, SHP465-112 or SHP465-309, will serve as the baseline visit (Visit 2) for analyses of this study. For subjects in Group B, a screening visit will precede a washout period. Data will be summarized using the following layouts:

- For full analysis, data will be summarized using the following 5 columns:
 - Antecedent Study:
 - Group A 112 SHP465 6.25mg
 - Group A 309 Placebo
 - Group A 309 SHP465 6.25mg
 - Direct Enrollment: Group B SHP465 6.25mg
 - Total
- For full analysis by-age group summaries, data will be summarized using the following 3 columns:
 - Group A Antecedent Study
 - Group B Direct Enrollment
 - Total

For all subjects in Group A and Group B, SHP465 will be administered as a daily morning dose of 6.25 mg in the treatment of ADHD.

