11. SAFETY ANALYSES

Safety data will be analyzed for the Safety Set by treatment group of the antecedent studies, current treatment (SHP465) for each enrollment type, and overall. Safety endpoints include the occurrence of TEAEs, vital signs (systolic and diastolic blood pressure, and pulse), height, weight, body mass index (BMI); clinical laboratory and ECG results, C-SSRS, and sleep questionnaires (PSQ and CSHQ). For each safety endpoint, the last value collected before the first dose of investigational product in this study will be used as baseline for all analyses of that safety endpoint. Except for adverse event data, only post-baseline assessments from Visit 2 (Week 0) up to Visit 16 (Month 12) that were collected on or 2 days after the last dose of investigational product will be analyzed. A Final on-Treatment Assessment (FoTA) will be defined as the last valid assessment obtained after Baseline and whilst on investigational product (on or before 2 days after the last dose date).

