11.3 Vital Signs (Including Height and Weight)

The averaged values of the 3 measurements collected for blood pressure and pulse at each visit will be used for all summaries and determination of PCIs. Summaries for vital signs will be presented by treatment group of the antecedent studies, current treatment (SHP465) for each enrollment type, and overall.

Descriptive statistics for vital signs (sitting systolic and diastolic blood pressure, pulse and weight) and their changes from baseline at each post-baseline visit and FoTA will be presented in a summary table. These summaries will also include BMI. BMI will be automatically

calculated using the height and weight collected at each visit. In the case of multiple assessments at post-baseline visits, the first readable value at the visit will be used in the summary tables.

Additionally, figures with the mean change from baseline \pm SD of the vital signs values (sitting systolic and diastolic blood pressure, and pulse) will be presented by visit for each treatment group of the antecedent studies and current treatment (SHP465) for each enrollment type.

Height, weight and BMI will also be converted to percentile values based on the subject's age and sex at each visit and summarized categorically (<5th, 5th to <95th, and \geq 95th) at each visit and at the FoTA. Post-baseline shifts in height, weight and BMI percentile category (<5th, 5th to <95th, and \geq 95th) from baseline will be summarized at each visit and at the FoTA. In addition, z-scores for weight and BMI will be based on the subject's age at each visit and will be summarized categorically (<-2, \geq -2 to <-1, \geq -1 to <1, \geq 1 to <2, and \geq 2) at each visit and at the FoTA. Percentiles and z-scores will be derived using the CDC growth charts ([Kuczmarski et al. 2002](#)). A SAS program for the 2000 CDC Growth Charts will be used to derive the percentiles and z-scores (www.cdc.gov/nccdphp/dnpao/growthcharts/resources/sas.htm).

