In addition, following the US Department of Health and Human Services standards, blood pressure values higher than the 95th percentile determined by sex, age, and height percentiles will be considered abnormal. The cut-off values are presented in [Table 9](#). If a height percentile falls between the listed percentiles, as a conservative approach the lower end of the percentiles will be used to identify the corresponding 95th percentile of blood pressures. If a height percentile is less than 5th percentile, the 5th percentile will be used to identify the corresponding 95th percentile of blood pressures.

Table 9 95th Percentile Cut-off Values of Blood Pressure Norms by Sex, Age, and Height Percentiles

Age (y)	Systolic Blood Pressure (mmHg)							Diastolic Blood Pressure (mmHg)							
	Percentile of Height							Percentile of Height							
Boys															
	5%	10%	25%	50%	75%	90%	95%		5%	10%	25%	50%	75%	90%	95%
4	106	107	109	111	112	114	115		66	67	68	69	70	71	71
5	108	109	110	112	114	115	116		69	70	71	72	73	74	74
6	109	110	112	114	115	117	117		72	72	73	74	75	76	76
7	110	111	113	115	117	118	119		74	74	75	76	77	78	78
8	111	112	114	116	118	119	120		75	76	77	78	79	79	80
9	113	114	116	118	119	121	121		76	77	78	79	80	81	81
10	115	116	117	119	121	122	123		77	78	79	80	81	81	82
11	117	118	119	121	123	124	125		78	78	79	80	81	82	82
12	119	120	122	123	125	127	127		78	79	80	81	82	82	83
Girls															
4	105	106	107	108	110	111	112		68	68	69	70	71	71	72
5	107	107	108	110	111	112	113		70	71	71	72	73	73	74
6	108	109	110	111	113	114	115		72	72	73	74	74	75	76
7	110	111	112	113	115	116	116		73	74	74	75	76	76	77
8	112	112	114	115	116	118	118		75	75	75	76	77	78	78
9	114	114	115	117	118	119	120		76	76	76	77	78	79	79
10	116	116	117	119	120	121	122		77	77	77	78	79	80	80
11	118	118	119	121	122	123	124		78	78	78	79	80	81	81
12	119	120	121	123	124	125	126		79	79	79	80	81	82	82

Source: National Heart Lung and Blood Institute; May 2004
http://www.nhlbi.nih.gov/guidelines/hypertension/child_tbl.htm

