The number and percentage of subjects with any post-baseline blood pressure values higher than the 95th percentile (exclusive) will be tabulated by gender and treatment group of the antecedent studies, current treatment (SHP465) for each enrollment type, and overall. The denominator will be the number of subjects in the Safety Set (per gender) with at least 1 post-Baseline blood pressure measurement. The numerator will be the total number of subjects with at least 1 blood pressure value higher than the 95th percentile. A supportive listing of all subjects with abnormal blood pressure values will be provided.

All vital signs data will be listed for the safety Set.

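### SAP 11.3 reports mean blood pressure change in raw mmHg only, so with no control arm small late-visit or final on-treatment rises cannot be separated from normal growth

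*SAP*

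**What the plan says.** SAP 11.3 summarises sitting systolic and diastolic pressure "and their changes from baseline at each post-baseline visit and FoTA will be presented in a summary table", and plots mean change with SD by visit. Both use the measured values.

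Norms for sex, age and height are applied to blood pressure in one place only: the number of children with "any post-baseline blood pressure values higher than the 95th percentile (exclusive) will be tabulated by gender". For a height between two listed percentiles, "as a conservative approach the lower end of the percentiles will be used to identify the corresponding 95th percentile of blood pressures".

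Height, weight and BMI are treated differently in the same section: "Percentiles and z-scores will be derived using the CDC growth charts". These are summarised by category, not as mean changes.

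SAP 2.1 offers an age-group layout ("For full analysis by-age group summaries, data will be summarized using the following 3 columns"), but 11.3 does not say that vital signs use it.

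For safety endpoints, SAP 11 says that "the last value collected before the first dose of investigational product in this study will be used as baseline". SAP 2.1 says instead that, for Group A, the baseline defined in the antecedent study serves for the analyses of this study.

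**The concern.** Blood pressure is part of the primary long-term safety objective (Protocol 2.2.1), and the late-visit and FoTA means carry the long-term message. Reference pressure rises with age in children of 4-12 years, and nothing in this single-treatment, open-label study separates that rise from a drug effect. The 95th-percentile count deals with high individual values. It cannot show or correct a mean shift inside the normal range.

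The pattern most easily misread is a slow late rise. Under the SAP 11 baseline, children who took SHP465 in the antecedent study may start from an on-drug value. Their initial drug effect is then already in the baseline, and a later rise of 1-2 mmHg may be mostly growth yet be read as a progressive drug effect. Under the SAP 2.1 baseline the growth interval is longer. For blood pressure the error is toward overstating harm.

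For scale, Protocol 1.2 reports a mean drug increase of about 2-4 mmHg, in a section that describes doses of 12.5 mg and above. A year of growth overlaps the lower part of that range.

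**Working it through.** The plan gives no figure to reproduce: sample size is not statistical and no test is planned (SAP 2.5, 2.6). The inputs are the reference tables in Protocol Appendix 2.3 (boys) and 2.5 (girls).

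**Check on reading the tables.** The footnote says "The 90th percentile is 1.28 SD, 95th percentile is 1.645 SD, and the 99th percentile is 2.326 SD over the mean". So SD = (95th - 50th)/1.645. For boys aged 8, systolic, 50th height percentile: (116 - 99)/1.645 = 10.33, and 99 + 1.28 x 10.33 = 112.2, against 112 printed.

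**Yearly steps**, 50th blood pressure percentile at the 50th height percentile, ages 4 to 13:
- Boys systolic: 2, 1, 1, 2, 1, 2, 2, 2, 2; mean 15/9 = 1.67
- Girls systolic: 2, 1, 2, 2, 2, 2, 1, 2, 2; mean 16/9 = 1.78
- Boys diastolic: 3, 2, 2, 2, 1, 1, 0, 1, 0; from ages 4-5, 5/2 = 2.5; from ages 6-12, 7/7 = 1.0
- Girls diastolic: 2, 2, 1, 1, 1, 1, 1, 1, 1; from ages 4-5, 4/2 = 2.0; from ages 6-12, 7/7 = 1.0

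**Expected change from growth alone** = yearly step x days/365.25. The factors are 30/365.25 = 0.082, 180/365.25 = 0.493 and 360/365.25 = 0.986.

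| mmHg | Per year | Month 1 | Month 6 | Month 12 |
|---|---|---|---|---|
| Systolic, ages 4-12 | 1.67-1.78 | 0.1 | 0.8-0.9 | 1.6-1.8 |
| Diastolic, ages 4-5 | 2.0-2.5 | 0.2 | 1.0-1.2 | 2.0-2.5 |
| Diastolic, ages 6-12 | 1.0 | 0.1 | 0.5 | 1.0 |

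The last row assumes an even age spread. For boys it averages 5/3 = 1.67 a year from ages 6-8 and 2/4 = 0.5 from ages 9-12.

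**Sensitivity to height.** Averaged over all seven height columns, the yearly steps are 1.70 (boys) and 1.81 (girls) systolic. Diastolic steps are 2.64 and 2.0 from ages 4-5, and 1.0 and 1.08 from ages 6-12. The single-column maximum is 3.0 diastolic, for boys aged 4-5.

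**Precision** (assumed SD of change 8-10 mmHg; the documents give none). SE of one mean = SD/sqrt(n). At the 6-month target of 60 children: 8/sqrt(60) = 1.0 to 10/sqrt(60) = 1.3, against a systolic drift of 0.8-0.9. With 20 children at Month 12, the count that SAP 14 had planned as an interim trigger: 8/sqrt(20) = 1.8 to 10/sqrt(20) = 2.2, against 1.6-1.8.

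**How far follow-up reaches.** SAP 1 dates the termination decision 14 Dec 2018. If dosing stopped that day (an assumption), Day 360 was reached only by children with baseline by 19 Dec 2017, and Day 180 by those with baseline by 17 Jun 2018. The original protocol is dated 11 Sep 2017. The documents do not say how many children reached either day. FoTA therefore mixes durations, and its expected drift cannot be read from the raw table.

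**The case against.** The strongest reply is that little hangs on this. No test or decision uses these means. The likely error is on the cautious side, and the drift is no larger than sampling error at the sizes that the documents suggest. The by-visit table also shows Weeks 1-2 and Month 1, where growth adds only 0.1-0.2 mmHg. In children who enter off drug (309 placebo and Group B), the early change is thus a nearly clean estimate. All of this stands and limits the point. It does not tell a reader whether a further late rise is growth or drug.

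The age-group layout might apply to vital signs in the separate table specifications, which cannot be judged here. In any case, splitting by age does not remove drift within an age group.

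Four stronger readings are tempting, and the documents do not support them:
- **That any mean rise up to 2-3 mmHg is uninterpretable.** Growth of that size applies only to diastolic pressure at ages 4-5 after a full year.
- **That the SAP adjusts other means for growth and left blood pressure out.** Weight and BMI norms are categorical, and their mean changes are raw too. A growth-adjusted mean would be a new type of output.
- **That age confounds the comparison of the 112 and 309 columns.** SAP 2.1 does say "Antecedent study SHP465-112 is a Phase 1 study in subjects aged 4-5 years who were administered 6.25 mg SHP465", and 309 took ages 6-12. But the expected diastolic gap at Month 12 is (2.5 - 1.67) x 0.986 = 0.8 to (2.5 - 0.5) x 0.986 = 2.0 mmHg. With 20-40 children per column (assumed), the SE of a difference is 8 x sqrt(2/40) = 1.8 to 10 x sqrt(2/20) = 3.2. The gap is within noise.
- **That pulse is unaffected.** The limits in SAP Table 8 fall with age; for boys the 99th percentile goes from 120 at 4-5 years to 108 at 12. Raw late pulse change may therefore understate a drug effect.

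**Conclusion.** The point holds as a minor one on interpretation. As planned, late-visit or FoTA mean rises of about 1-2 mmHg, or up to about 2.5 mmHg diastolic at ages 4-5 after a full year, cannot be attributed to SHP465. Month 12 drift is a ceiling because of early termination. Early changes, clearly larger mean rises and individual elevations can be interpreted as planned.

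A reader should not infer that the plan would miss clinically important hypertension. The 95th-percentile count and the potentially clinically important criteria address that.

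The sizes assume that cross-sectional reference medians describe growth at a constant height percentile, that growth is linear within a year, and that ages within each group are evenly spread. The comparison with sampling error also rests on the assumed SD of change.

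**What to change.** In SAP 11.3, beside the raw change, add by visit and at FoTA the mean change from baseline in observed minus tabulated 50th-percentile pressure for age at visit, sex and height percentile. Do this for systolic and diastolic pressure, from Protocol Appendix 2.3 and 2.5. The equivalent z-score would also serve, with SD = (95th - 50th)/1.645. A full-year systolic drift of 1.6-1.8 mmHg is about 0.15-0.17 SD on that scale, and its expected value after adjustment is zero.

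Interpolate linearly in age and height percentile. The lower-percentile rule used for Table 9 would add steps of up to 2 mmHg systolic when a child crosses a listed percentile. Use the end columns outside the 5th-95th height percentiles, and the rows above age 12 where needed.

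State which baseline applies to Group A, that of SAP 11 or SAP 2.1. It sets both the growth interval and whether the baseline is on drug.

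Footnote the pulse table: reference limits fall with age, so a raw late change may understate a drug effect.

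The cost is SAP wording, two derived variables and a few table rows. SAP 11.3 already derives height percentile for age at each visit, and the medians are printed. The adjustment relies on whole-number medians, and it does not address dropout or the lack of a control.

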3. OBJECTIVES

3.1 Primary Objective

The primary objective is to evaluate the long-term safety and tolerability of SHP465 at 6.25mg administered as a daily morning dose in children aged 4-12 years (inclusive at the time of consent) diagnosed with Attention-deficit/Hyperactivity Disorder (ADHD).

The evaluation of safety and tolerability will be based on the occurrence of treatment-emergent adverse events (TEAEs), evaluation of vital signs (systolic and diastolic blood pressure and pulse), weight, height, body mass index (BMI); clinical laboratory and electrocardiogram (ECG) results; sleep assessment (Post Sleep Questionnaire [PSQ], and Children's Sleep Habits Questionnaire [CSHQ]); and responses to the Columbia-Suicide Severity Rating Scale (C-SSRS).

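### Weight and BMI z-scores are reported only as unpaired counts in five bands, so a small to moderate average fall in age-adjusted weight or BMI can go unseen; the mean change should be added

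*SAP*

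**What the plan says.** SAP 3.1 puts these measures in the primary safety objective ("weight, height, body mass index (BMI" and so on). SAP 11.3 then plans the following outputs for them.

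- **z-scores (weight and BMI).** These use the subject's "age at each visit and will be summarized categorically". The cut points are -2, -1, 1 and 2, at each visit and at the final on-treatment assessment (FoTA). The values exist on a continuous scale before they are cut: "Percentiles and z-scores will be derived using the CDC growth charts", with a CDC SAS program.
- **Percentiles (height, weight and BMI).** There are three classes: below the 5th, 5th to below the 95th, and 95th or above. Shifts are planned for these: "Post-baseline shifts in height, weight and BMI percentile category" from baseline, at each visit and FoTA.
- **Raw values.** "Descriptive statistics for vital signs (sitting systolic and diastolic blood pressure, pulse and weight) and their changes from baseline" are summarised at each post-baseline visit and FoTA, and "These summaries will also include BMI".
- **Potentially clinically important (PCI) flags.** Tables 6 and 7 flag a weight loss of 7% or more. Table 6, for ages 4-5, also flags weight gain of 7% or more and BMI below the 5th or above the 95th percentile for age and sex.
- **Figures.** Plots of mean change are limited to part "of the vital signs values (sitting systolic and diastolic blood pressure, and pulse) will be presented by visit", so weight and BMI have none.

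SAP 18.1 gives a general rule that continuous variables get n, mean, median, SD, minimum and maximum.

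**The concern.** In growing children the useful question is whether weight and BMI keep pace with age norms, and the z-score is the derived variable that answers it. The plan reports it only as the number of children in each band at each visit. The middle band is 2 SD wide, and the counts are not paired with the child's own baseline, so movement between bands is mixed with children leaving the study.

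Decreased weight and decreased appetite are listed as known effects in Protocol 1.2 and are events of clinical interest in SAP 11.1.1. If the group drifted modestly below its age norm, the report might contain no summary that shows it.

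**Working it through.** The documents give no figure to reproduce. The sample size has no statistical basis (SAP 2.5), no effect or SD is assumed, and no test is planned (SAP 2.6). The check is first a comparison of outputs, then an illustration.

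**Step 1: can another planned output show an average age-adjusted change?**

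| Output | Age-adjusted | Paired with baseline | Continuous |
|---|---|---|---|
| z-score bands | yes | no | no |
| Percentile classes and shifts | yes | yes | no |
| Raw weight and BMI, with change | no | yes | yes |
| 7% weight flags | no | yes | no |
| BMI percentile flag, ages 4-5 | yes | no | no |

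No row has all three properties.

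**Step 2: how coarse are the classes?** On the standard normal scale, z = 0.95 is the 83rd percentile and z = -0.95 the 17th. A child can fall by 1.90 z and stay in the middle z band. The 90th percentile is z = 1.28 and the 6th is z = -1.55. A fall between them, 1.28 + 1.55 = 2.83 z, is no shift in the percentile table.

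**Step 3: illustration for weight.** Inputs:
- n = 60, the target for children completing 6 months (Protocol 9.6, SAP 2.5), set before termination.
- Baseline z normal with mean 0 and SD 1, cut at -1.645 because exclusion criterion 8 removes weight at or below the 5th percentile. The distribution is an assumption.
- SD of within-child change 0.3 to 0.5, and mean fall 0.2 or 0.3 z. Both are assumptions.

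Precision of the mean change: half-width of the 95% CI = 1.96 × SD / √60. For SD 0.3 this is 1.96 × 0.3 / 7.746 = 0.076. For SD 0.5 it is 1.96 × 0.5 / 7.746 = 0.127. A fall of 0.2 z is then 0.2 / (0.3 / 7.746) = 5.2 or 0.2 / (0.5 / 7.746) = 3.1 standard errors from zero.

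What the percentile shift table would hold for the same fall: 93.7% (SD 0.3) or 90.3% (SD 0.5) of children stay in their class. About 60 × 0.063 = 3.8 or 60 × 0.097 = 5.8 children change class.

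What the z-band counts would hold, lowest to highest band, SD 0.3: 0 / 6.9 / 43.2 / 8.5 / 1.4 at baseline becomes 0.5 / 10.4 / 41.3 / 6.8 / 1.1. No band moves by more than 3.5 children.

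As one yardstick, simulated chance of detection at two-sided 5%: a one-sample t test on the change, against a sign test on children moving down versus up a class.

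| Mean fall | Mean z change | Percentile-class shifts (planned table) | z-band shifts (not planned) |
|---|---|---|---|
| 0.2 z | 86-99.9% | 10-15% | about 35-50% |
| 0.3 z | not needed: 4.6 to 7.7 standard errors | about 28-31% | about 70-87% |

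The standard errors in the last row are 0.3 / (0.5 / 7.746) = 4.6 and 0.3 / (0.3 / 7.746) = 7.7.

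**Step 4: sensitivity to n.** With 20 children the half-width is 1.96 × 0.3 / √20 = 0.131 to 1.96 × 0.5 / √20 = 0.219. The mean change is then less precise, but its uncertainty is stated, which band counts do not do.

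**The case against.** The strongest defence is that the study is descriptive and uncontrolled, that no test is planned, and that weight is already covered in several ways. There are percentile classes with shifts, raw changes at every visit, 7% weight-loss flags with listings, detailed summaries of weight decrease and decreased appetite (SAP 11.1.1), and a listing of all vital signs. This stands as far as individual weight loss goes. It does not supply a group-level age-adjusted change: the 7% rule flags absolute loss, so a child who merely stops gaining is not flagged, and a positive mean raw change can coexist with a falling z-score.

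SAP 18.1 could be read as supplying the mean anyway, and table specifications are in a separate document. But 11.3 gives a specific categorical rule for z-scores, which the general convention does not clearly override. What is established is that the SAP text plans no mean; the table shells cannot be checked here.

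Three limits on the illustration also stand. It applies a test that the SAP does not plan. The cut at the 5th percentile comes from a criterion on weight, so it does not describe BMI. And 60 is the target before termination; SAP 1 records that the sponsor stopped the study on 14 December 2018, so the number at later visits is unknown.

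A reader might infer that the z bands are the only age-standardised result, or that any clear drift will be missed. The documents support neither. Percentile classes, their shifts and the BMI flag at ages 4-5 are age-standardised too. Larger drifts do become visible in bands: even at 0.3 z, a z-band shift table would pick up the fall about 70-87% of the time. Nor is the absence of a cited reason for the bands a defect, since nothing in the documents requires one.

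**Conclusion.** The point holds as a free improvement, not as an error or contradiction. For two variables in the primary safety objective, the SAP text plans no summary that is age-adjusted, paired with baseline and continuous, although the z-scores needed for one are derived. A small to moderate average fall can go unseen.

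For weight, the loss is largest at about 0.2 z and narrows as the fall grows. The size rests on assumed values (60 children, SD of change 0.3-0.5, normal baseline) and should be read as a range. No figure is claimed for BMI, though the same reasoning about coarse classes and growth applies.

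**What to change.** In SAP 11.3, add for the weight and BMI z-scores: n, mean, SD, median, minimum and maximum, and mean change from baseline with a 95% CI, at each visit and at FoTA, in the existing columns. Keep the five bands as a supplement and add a baseline-to-FoTA shift table for them.

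The cost is a small amount of extra programming and output from variables the CDC program already produces. It needs no new data, no protocol change and no test. A 95% CI on a descriptive change also matches what SAP 10.2.1 already does for the ADHD-RS-5 total score.
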